5.3 MISSING DATA HANDLING

No imputation of values for missing data will be performed except that missing or partial start and end dates for AEs and concomitant medication will be imputed according to prespecified, conservative imputation rules. Subjects lost to follow-up (or drop out) will be included in statistical analyses to the point of their last evaluation.

5.4 ENDPOINT DATA ANALYSIS

5.4.1 Safety Endpoint

Safety summaries will include summaries in the form of tables and listings. The frequency (number and percentage) of treatment emergent AEs and events of clinical interest will be reported in each treatment group by Medical Dictionary for Regulatory Activities (MedDRA) System Organ Class and Preferred Term. Summaries will also be presented by the severity of the AE (per Common Terminology Criteria for Adverse Events [CTCAE], v4.03 or higher) and by relationship to study drug (eg, either acalabrutinib, pembrolizumab, or both).

Laboratory shift tables containing counts and percentages will be prepared by treatment assignment, laboratory parameter, and time. Summary tables will be prepared for each laboratory parameter. Figures of changes in laboratory parameters over time will be generated.

Results of vital sign assessments and physical exams will be tabulated and summarized.

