3.0 STUDY DESIGN

This clinical trial is a Phase 2, multicenter, open-label, randomized study evaluating pembrolizumab monotherapy and the combination of acalabrutinib and pembrolizumab in subjects who have recurrent or metastatic NSCLC.

Subjects meeting the eligibility criteria for the study will be randomized 1:1 to one of the following arms:

Arm 1: Pembrolizumab 200 mg administered as an IV infusion every 3 weeks (Q3W)

Arm 2: Acalabrutinib 100 mg administered PO BID plus pembrolizumab 200 mg IV Q3W

Acalabrutinib treatment can continue for subjects who are tolerating therapy and not progressing. Pembrolizumab treatment is for 24 months from the date of first dose for subjects who are tolerating therapy and not progressing. Subjects who progress on the combination of pembrolizumab and acalabrutinib will discontinue study treatment while those with progression of disease in the pembrolizumab monotherapy arm will continue on pembrolizumab with the addition of acalabrutinib until a second disease progression or intolerance to therapy. For subjects who cross over to receive combination treatment, acalabrutinib treatment will begin at the next visit at which subjects are scheduled to receive pembrolizumab. The dose of acalabrutinib for these subjects will be determined based on the DLT review of Arm 2. Disease progression will be determined based on irRECIST guidelines ([Appendix 8](#) and detailed in [Section 3.11](#)).

[figure not shown]
Pembrolizumab treatment can end for subjects with confirmed CR if treatment has been administered for at least 24 weeks and 2 doses of pembrolizumab have been administered after confirmation of CR. Treatment on this protocol can continue for a minimum of 12 months after the last subject is randomized.

All subjects will have hematology, chemistry, and urinalysis safety panels performed at screening. Once dosing commences (Day 1), all subjects will be evaluated for safety, including serum chemistry, serum amylase and lipase, and hematology. PD and PK testing will be performed during the first few months of treatment. Radiologic tumor assessments will be completed at baseline and at ~6-week intervals during the trial. Subjects who discontinue study drug for any reason other than disease progression,

death, lost to follow-up, or withdrawal of consent will be followed for tumor assessment until disease progression or initiation of any other anticancer therapies, whichever comes first.

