3.3.4 Enrollment and Randomization Procedures

Enrollment of a subject into the study will be performed according to the following procedure:

The study center will notify the sponsor when a clinically eligible subject is identified and is ready to screen, to ensure enrollment availability on the study.

After the subject has signed and dated the Informed Consent Form (ICF), all screening procedures have been completed, and eligibility has been confirmed, the subject can be officially enrolled into the study.

To enroll a subject, the study center will fax/email a completed Enrollment Confirmation Form to the sponsor. The enrollment date will be the date that the sponsor confirms enrollment. The sponsor will aim to fax/email a completed Enrollment Confirmation Form to the study center within 24 hours.

The treatment assignment is based on the randomization list generated by the sponsor before study enrollment begins.

The Enrollment Confirmation Form will contain treatment-arm allocation.

Treatment must begin within the screening window ([Section 4.1](#)) and after the site has received the treatment-arm allocation from the sponsor.

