3.11 TREATMENT AFTER INITIAL RADIOLOGIC PROGRESSION

RECIST 1.1 will be adapted to account for the unique tumor response characteristics seen with treatment of pembrolizumab. Immunotherapeutic agents such as

pembrolizumab may produce antitumor effects by potentiating endogenous cancer-specific immune responses. The response patterns seen with such an approach may extend beyond the typical time course of responses seen with cytotoxic agents and can manifest a clinical response after an initial increase in tumor burden or even the appearance of new lesions. Standard RECIST may not provide an accurate response assessment of immunotherapeutic agents such as pembrolizumab. Therefore, RECIST 1.1 will be used with the following adaptations:

- If radiologic imaging verifies initial disease progression, tumor assessment should be repeated ≥ 4 weeks later to confirm disease progression with the option of continuing treatment per below.
- If repeat imaging shows $< 20\%$ tumor burden compared to nadir, stable or improved previous new lesion (if identified as cause for initial disease progression), and stable/improved non-target disease (if identified as cause for initial disease progression), treatment may be continued / resumed.
- If repeat imaging confirms disease progression due to any of the scenarios list below, subjects will be discontinued from study therapy (except subjects who cross over to receive acalabrutinib in addition to pembrolizumab).

In determining whether or not the tumor burden has increased or decreased, site study team should consider all target lesions as well as non-target lesions (if needed, the tip sheet provided in the study binder can be used as a reference to assess lesions).

Scenarios where disease progression is confirmed at repeat imaging:

- Tumor burden remains $\geq 20\%$ and at least 5 mm absolute increase compared to nadir
- Non-target disease resulting in initial disease progression is worse (qualitative)
- New lesion resulting in initial disease progression is worse (qualitative)
- Additional new lesion(s) since last evaluation

In subjects who have initial evidence of radiological disease progression, it is at the discretion of the treating physician whether to continue a subject on study treatment until repeat imaging is obtained. This clinical judgment decision should be based on the subject's overall clinical condition, including performance status, clinical symptoms, and

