4.1.19 Tumor Assessments

A pretreatment computerized tomography (CT) scan with contrast (unless contraindicated) is required of the chest, abdomen, and pelvis and any other disease sites (eg, neck) within 30 days before the first dose of study drug.

On-treatment CT scans with contrast (unless contraindicated) of the chest, abdomen, and pelvis and any other disease sites (eg, neck) will be done for tumor assessments at Week 7, 13, 19 (\pm 7 days) then every 12 weeks (\pm 10 days) thereafter or more frequently at investigator discretion. At all other visits, tumor assessments will be done by physical exam and laboratory results.

RECIST 1.1 guidelines ([Eisenhauer 2009](#)) will be followed for selection of measurable and nonmeasurable lesions and also with regard to the number of lesions to be assessed (refer to [Appendix 7](#) for more details on RECIST 1.1). Response will also be assessed by irRECIST (refer to [Appendix 8](#) for more details).

De-identified copies of all radiology results may be requested by the sponsor.

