5.2 DEFINITION OF ANALYSIS POPULATIONS

The following definitions will be used for the efficacy and safety analysis populations.

All-treated population: All enrolled subjects who receive ≥ 1 dose of any study drug (either acalabrutinib or pembrolizumab). The safety and primary efficacy analyses will be performed on the All-treated population.

Efficacy-evaluable population: All subjects in the All-treated population who have ≥ 1 evaluable response assessment after the first dose of study drug (either acalabrutinib or pembrolizumab). Sensitivity analyses for efficacy will be carried out on the Efficacy-evaluable population.

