Appendix 5. Schedule of Assessments – Crossover

Treatment Phase (Weeks)					
Weeks After Crossover ^{a,b}	0	1	2	3	≥ 4
Study Window	± 3 days				
Vital signs		X	X		
Lab assessments:					
Hematology ^c	X	X			
Serum chemistry ^d	X	X			
Study drug compliance	X	X			
Concomitant medications	X	X			
Adverse events	X	X			
Acalabrutinib 100 mg BID ^b	X	X	X	X	
Pembrolizumab 200 mg Q3W	X				X

Abbreviations: BID = twice per day; Q3W = every 3 weeks.

Footnotes for ACE-ST-007 Schedule of Study Activities - Crossover:

- Subjects are to complete assessments as shown in the 2 weeks following crossover. (Eg, if a subject crosses over to receive acalabrutinib and pembrolizumab at Week 10, assessments will be performed as listed for Week 10 in [Appendix 4](#). During Weeks 11 and 12, assessments will be performed as listed above for Weeks 1 and 2 after crossover. During Week 13, assessments will be performed as listed in Week 13 in [Appendix 4](#); assessments will be performed as listed in [Appendix 4](#) for all subsequent weeks).
- Subjects who cross over to receive acalabrutinib in addition to pembrolizumab should start acalabrutinib treatment at the next visit in which they are scheduled to receive pembrolizumab.
- Hematology includes complete blood count with differential and platelet and reticulocyte counts.
- Serum chemistry: albumin, alkaline phosphatase, alanine transaminase (ALT), aspartate aminotransferase (AST), bicarbonate, blood urea nitrogen (BUN), bone-specific alkaline phosphatase, calcium, chloride, creatinine, glucose, lactate dehydrogenase (LDH), magnesium, phosphate, potassium, sodium, total bilirubin, total protein, and uric acid.

Product: Acalabrutinib (ACP-196)

Date: 23 May 2016

Protocol: ACE-ST-007

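### Laboratory shift tables grouped by randomized arm, with no cut at crossover, put on-combination AST/ALT shifts in the pembrolizumab monotherapy column

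*Protocol*

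**What the plan says.** Section 5.4.1 fixes the layout: "Laboratory shift tables containing counts and percentages will be prepared by treatment assignment, laboratory parameter, and time". Section 3.3.4 says what the assignment rests on: "The treatment assignment is based on the randomization list generated by the sponsor before study enrollment begins". Section 3.5.1 titles Arm 1 as pembrolizumab monotherapy.

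Section 5.2 names the analysis set: "The safety and primary efficacy analyses will be performed on the All-treated population". Sections 5.2 to 5.4.1 define no crossover period, no crossover group and no new baseline. The only stated limit on data, in Section 5.3, is the last evaluation of subjects who drop out or are lost to follow-up.

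Crossover is part of the design. Under Section 3.0, "those with progression of disease in the pembrolizumab monotherapy arm will continue on pembrolizumab with the addition of acalabrutinib", and for these subjects "acalabrutinib treatment will begin at the next visit at which subjects are scheduled to receive pembrolizumab". Appendix 5 adds serum chemistry, including AST and ALT, after crossover. Its example is a subject who crosses over at Week 10: "During Weeks 11 and 12, assessments will be performed as listed above for Weeks 1 and 2 after crossover". From Week 13 that subject returns to the Appendix 4 schedule.

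**The concern.** The randomized arm does not change when a subject crosses over, but the exposure does. A table grouped by randomized arm and carried past crossover therefore reports combination data in the monotherapy column.

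This bears on the laboratory signal the protocol itself singles out. Section 3.10.1 warns that transaminase elevations may be more frequent and more severe on the combination than on pembrolizumab alone. The Summary of Amendment 4 gives this signal as the reason for the extra crossover assessments. Read as written, Section 5.4.1 files the results of those assessments under the comparator. Characterising safety is a primary objective (Section 2.1), and the shift tables are where graded AST and ALT changes would be compared between arms.

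**Working it through.** The protocol gives no figure to reproduce here. The check is where, on the protocol's own calendar, the stated grouping goes wrong, and in which direction.

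**Inputs**
- Pembrolizumab every 3 weeks from Week 1, with chemistry every 3 weeks from Week 10 (Appendix 4). The shared visits are Weeks 1, 4, 7, 10, 13, 16, 19, 22, 25 and 28.
- CT scans "will be done for tumor assessments at Week 7, 13, 19" with a window of 7 days either way (Section 4.1.19).
- Confirmation: "tumor assessment should be repeated ≥ 4 weeks later to confirm disease progression" (Section 3.11). The Synopsis makes confirmed progression the trigger for adding acalabrutinib.
- Acalabrutinib starts at the next pembrolizumab visit (Section 3.0).
- Extra chemistry in Weeks 1 and 2 after crossover (Appendix 5). The table is damaged in the available text, but its first footnote and the chemistry row support this reading.

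**Rule:** crossover week = first pembrolizumab week at or after scan week + 4. The chemistry value at the crossover visit itself is taken as drawn before the first acalabrutinib dose.

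| Scan showing progression | Earliest confirmation | Crossover | Extra chemistry | First shared visit on combination |
|---|---|---|---|---|
| Week 7 | 7 + 4 = 11 | 13 | 14, 15 | 16 |
| Week 13 | 13 + 4 = 17 | 19 | 20, 21 | 22 |
| Week 19 | 19 + 4 = 23 | 25 | 26, 27 | 28 |

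**The Appendix 5 example (crossover at Week 10).** Week 7 starts on Day 6 × 7 + 1 = 43, and Week 10 on Day 9 × 7 + 1 = 64. A scan 7 days early falls on Day 36, and 36 + 28 = 64, which just reaches Week 10. Using the 3-day visit window (Day 67), a scan as late as Day 67 − 28 = 39, that is 4 days early, also reaches it. A scan 3 days early or less leads to Week 13. In the example the extra chemistry falls in Weeks 11 and 12, and mixing starts at Week 13.

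**What the time split does**
1. *Before crossover:* the Arm 1 rows are clean.
2. *Extra crossover weeks:* none is a 3-weekly chemistry week. Setting aside unscheduled, early-termination and safety follow-up draws, the Arm 1 values in those weeks come only from crossed-over subjects, and Arm 2 has no scheduled chemistry there. These rows are not diluted; they are combination data in the monotherapy column.
3. *Shared 3-weekly visits after crossover:* both exposures fall in one Arm 1 row.

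**Direction at a shared visit.** Let m be the crossed-over share of the Arm 1 values at that visit. Let p1 and px be the rates of a given shift on monotherapy and after crossover, and p2 the rate in Arm 2.

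- Arm 1 row as tabulated: (1 − m)·p1 + m·px
- Contrast as tabulated: p2 − (1 − m)·p1 − m·px = (p2 − p1) − m·(px − p1)

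The contrast loses m·(px − p1). This is zero before crossover (m = 0) and positive afterwards whenever px exceeds p1. The protocol gives none of m, p1 or px at a visit, so no number follows.

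**The case against.** The strongest reply is that period definitions, re-baselining and crossover columns are ordinary content of a statistical analysis plan, which is not shown here, and that the sentence does not forbid a cut. That would answer a complaint about silence. Section 5.4.1, however, states a grouping. Section 5.4.4 expressly leaves the censoring rules for duration of response and PFS to the SAP, and Section 5.4.1 makes no such deferral for the shift tables. A SAP that cut at crossover would be going beyond the protocol or departing from it.

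A second reply is that treatment assignment might mean current treatment. Section 3.3.4 ties the term to the randomization list; if another meaning is intended, the sentence still needs correcting.

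A third is that the signal will surface elsewhere, through adverse events summarised by severity and by relationship to each drug, and through events of clinical interest. This helps only in part. A laboratory value becomes an adverse event only if the investigator judges it clinically significant (Section 6.1.1). The hepatic event of clinical interest needs AST or ALT of at least 3 times ULN together with bilirubin of at least 2 times ULN and alkaline phosphatase below 2 times ULN (Section 6.2.5). Transaminase shifts short of these appear only in the laboratory tables.

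Three points stand. The rows for the extra weeks are mislabelled rather than diluted. The tables are descriptive and drive no test or decision rule. The size is unknown. They limit the weight of the concern without removing the mixing at shared visits.

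**Conclusion.** The concern holds. The stated grouping attributes on-combination laboratory values to Arm 1 after crossover. Nominally, Arm 1 rows made up only of crossover values begin at Week 14 and mixed rows at Week 16; in the Appendix 5 example they begin at Weeks 11 and 13.

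Only the direction can be given: a narrowed Arm 1 versus Arm 2 contrast at later visits, on the condition that the combination does raise transaminases. The calendar assumes crossover after confirmed progression on a scheduled scan. Section 4.1.19 allows more frequent scans, so individual crossovers may fall at other weeks.

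Arm 1 rows before crossover, Arm 2 rates, the DLT review and the Arm 2-only stopping rule in Section 5.5 are unaffected. This should be corrected because it touches a primary objective and costs little, but it does not threaten the trial's decisions.

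**What to change.** Amend the sentence in Section 5.4.1 so that:

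- laboratory shifts are tabulated by the treatment being received when the value was obtained;
- the Arm 1 monotherapy tables end at the first acalabrutinib dose;
- later values form a separate Arm 1 crossover group, timed in weeks after crossover as Appendix 5 already counts them, with the last value before that dose as the shift baseline.

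A supplementary table of shifts from the original baseline could be kept for the crossover group. For consistency, apply the same cut to the summaries of adverse events and events of clinical interest; their grouping wording is less definite, and the point about the laboratory tables does not depend on it.

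The cost is one sentence and a date cut in the table programs. The drug diary records acalabrutinib dose times (Section 3.4.4), Appendix 5 defines Week 0 of crossover, and crossover subjects must be identified anyway for the exploratory efficacy objective in Section 2.3. No visit, sample or treatment changes. The drawbacks are a few more table columns and a small crossover group.

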5.4.2 Demographics and Baseline Characteristics

Additional analyses will include summaries of subject demographics, baseline characteristics, compliance, and concurrent treatments. Concomitant medications will be coded and tabulated according to the World Health Organization Drug Dictionary (WHODRUG).

5.4.3 Study Treatment Administration and Compliance

Descriptive information will be provided regarding the number of acalabrutinib and pembrolizumab doses prescribed, the total number of doses taken, the number of days of treatment, and the number and timing of prescribed dose reductions and interruptions.

For each subject, acalabrutinib and pembrolizumab compliance will be described in terms of the proportion of study drug actually taken.

5.4.4 Analysis of Efficacy Parameters

Disease Control and Response Rate

The individual and composite endpoints of response and progression will be determined. Tumor control will be documented at each assessment by response category (see [Section 4.2](#)) as defined for each response parameter, date that response is first documented, and date of disease progression. DCR will be defined as the proportion of subjects who achieve a SD, PR or CR. ORR will be defined as the proportion of subjects who achieve a CR or PR (see [Section 4.2](#)).

DCR and ORR will be calculated and the corresponding 2-sided 95% CI will be derived.

In addition to evaluation of DCR and ORR by RECIST 1.1 criteria ([Eisenhauer 2009](#)), these endpoints will also be evaluated by irRECIST criteria ([Appendix 8](#)), though the ORR by RECIST will be considered the primary endpoint.

Duration of Response

The duration of response (DOR) is defined as the interval from the first documentation of response to the earlier of the first documentation of definitive disease progression or death from any cause. Kaplan-Meier methods will be used to estimate event-free curves and corresponding quartiles (including the median). Data from surviving, non-progressing subjects will be censored and detailed censoring rules will be specified in the statistical analysis plan (SAP).

Progression-free Survival

Progression-free survival (PFS) is defined as the interval from the date of first dose of study drug to the earlier of the first documentation of objective disease progression or death from any cause. Kaplan-Meier methods will be used to estimate the event-free curves and corresponding quartiles (including the median). Data from surviving, non-progressing subjects will be censored and detailed censoring rules will be specified in the SAP.

Overall Survival

OS is defined as the time from date of the first dose of study drug until date of death due to any cause. Subjects who are known to be alive or whose survival status is unknown will be censored at the date last known to be alive. The analysis methods for overall survival will be similar to those described for progression-free survival.

5.4.5 PD or Biomarker Analyses

Additional pharmacodynamic, pharmacokinetic and biomarker analyses may be performed, as deemed appropriate.

Correlations between subject characteristics and outcome measures and correlations among outcomes measures will be explored using regression models or other appropriate techniques.

5.5 FUTILITY AND TOXICITY MONITORING

The futility and toxicity monitoring will be analyzed in the combination arm (Arm 2) only as data become available. Futility will be monitored by irDCR, which is defined as irCR, irPR, and irSD by irRECIST ([Appendix 8](#)). irDCR of at least 20% is clinically meaningful in this population. The response outcome within the 12 weeks will be used in the futility analyses. A Bayesian method ([Thall 1995](#)) will be used for futility and toxicity monitoring for the combination arm. The stopping rules are:

- $\Pr(\theta_E < 0.20 | \text{data}) > 0.95$
- Or
- $\Pr(T_E > 0.30 | \text{data}) > 0.90$

Enrollment in the combination arm will be stopped early if there is > 95% probability that the irDCR is < 20% or there is > 90% probability that the toxicity rate is higher than 30% in that arm. Where θ_E denotes the marginal response rate, assuming that θ_E follows a prior distribution of beta (a, b), where a and b represent response and nonresponse

rates (0.2, 0.8), and T_E denotes the marginal toxicity rate, assuming that T_E has a prior distribution of beta (a, b), where a and b represent toxicity and no toxicity (0.3, 0.7). The definition of toxicity will follow the same definition used for assessing DLTs (see [Section 3.7](#)) including the DLT assessment window.

The above futility and toxicity monitoring rules will be implemented once the first 10 subjects have been evaluated in the combination arm and will use safety data as they become available. The corresponding stopping boundaries for the futility monitoring are: enrollment will be stopped early due to futility if (number of subjects with irDCR/number subjects evaluated) \leq 0/(10-15), 1/(16-23), 2/(24-30) and 3/(31-37). The corresponding stopping boundaries for toxicity monitoring are listed in [Table 5-1](#).

The operating characteristics of the design are presented in [Table 5-2](#). Multc Lean software V2.1 was used for the design.

Table 5-1. Stopping Boundaries for Toxicity Monitoring

	Stop enrolling if there are this many DLTs total:
No. Subjects (inclusive)	# Toxicities (inclusive)
1-9	Never stop with this many subjects
10-12	6-12
13-14	7-14
15-17	8-17
18-20	9-20
21-23	10-23
24-25	11-25
26-28	12-28
29-31	13-31
32-34	14-34
35-36	15-36
37	Always stop due to maximum sample size

Table 5-2. Operating Characteristics of the Design

irDCR	Toxicity rate	Probability of early stop	Average # of subjects treated
0.2	0.1	0.23	32.1
0.2	0.3	0.41	28.2
0.2	0.5	0.95	14.8
0.3	0.1	0.05	35.9
0.3	0.3	0.28	31.3
0.3	0.5	0.94	15.5

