the tip sheet provided in the study binder can be used as a reference to assess lesions). Subjects that are deemed clinically unstable are not required to have repeat tumor imaging for confirmation. If radiologic progression is confirmed by subsequent scan then the subject will be discontinued from trial treatment (or if on pembrolizumab alone arm may be eligible for cross over to receive acalabrutinib in addition to pembrolizumab). If radiologic progression is not confirmed, then the subject should resume or continue assigned treatment and have their next tumor imaging according to the protocol schedule.

NOTE: If a subject has confirmed radiographic progression (ie, 2 scans at least 4 weeks apart demonstrating progressive disease) per irRECIST, but the subject is achieving a clinically meaningful benefit, an exception to continue treatment may be considered following consultation with the sponsor.

irRECIST data will be collected in the clinical database.

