3.12 WITHDRAWAL OF SUBJECTS FROM STUDY TREATMENT

Any subject has the right to withdraw from the study at any time.

- Study treatment should be discontinued in the event of a toxicity lasting > 28 consecutive days, unless reviewed and approved by the medical monitor.
- Any subject who has confirmed objective evidence of cancer progression while receiving acalabrutinib and pembrolizumab should discontinue study treatment.
Note: Study subjects receiving immunotherapies can experience transient immunotherapy-related increases in lesion size (“pseudoprogression”) preceding tumor regression ([Hodi 2010](#)). If there is uncertainty regarding whether there is true cancer progression, the subject may continue study treatment and remain under close observation (eg, evaluated at 4-week intervals) pending confirmation of progression ([Section 3.11](#)). In particular, transient worsening of disease early in therapy or during temporary interruption of study therapy (eg, for drug-related toxicity, surgery, or intercurrent illness) may not indicate cancer progression. In such circumstances, and if medically appropriate, subjects may resume therapy and relevant clinical, laboratory, and/or radiographic assessment can be attempted to document whether tumor control can be maintained or whether cancer progression has occurred.
- Any subject whose medical condition substantially changes after entering the study should be carefully evaluated by the investigator in consultation with the

medical monitor. Such subjects should be withdrawn from study treatment if continuing would place them at risk.

- Any subject who becomes pregnant should be removed from study treatment.
- Any subject who becomes significantly noncompliant with study drug administration, study procedures, or study requirements should be withdrawn from study treatment in circumstances that increase risk or substantially compromise the interpretation of study results.
- The investigator, in consultation with the medical monitor, may withdraw any subject from study treatment, if, in the investigator's opinion, it is not in the subject's best interest to continue.

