7.0 STUDY ADMINISTRATION AND INVESTIGATOR OBLIGATIONS

Acerta Pharma retains the right to terminate the study and remove all study materials from a study site at any time. Specific circumstances that may precipitate such termination are:

- Unsatisfactory subject enrollment with regard to quality or quantity
- Significant or numerous deviations from study protocol requirements, such as failures to perform required evaluations on subjects and maintain adequate study records
- Inaccurate, incomplete and/or late data recording on a recurrent basis
- The incidence and/or severity of AEs in this or other studies indicating a potential health hazard caused by the study treatment

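### A Section 5.5 toxicity stop closes Arm 2 enrolment but leaves crossover from Arm 1 to the same combination open

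*Protocol*

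**What the plan says.** Section 5.5 of the protocol monitors futility and toxicity in Arm 2 only, starting once 10 subjects have been evaluated there. Its consequence is stated once for both rules: "Enrollment in the combination arm will be stopped early", in the toxicity case when "or there is > 90% probability that the toxicity rate is higher than 30% in that arm". Table 5-1 gives the boundaries under the heading "Stop enrolling if there are this many DLTs total". No other action is listed.

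Section 3.0 provides a second route onto the combination: "those with progression of disease in the pembrolizumab monotherapy arm will continue on pembrolizumab with the addition of acalabrutinib". The synopsis repeats this, and Appendix 5 schedules it at acalabrutinib 100 mg BID. Section 3.11 is softer, saying that subjects on pembrolizumab alone with confirmed progression "may be eligible for cross over to receive acalabrutinib in addition to pembrolizumab", but it attaches no safety condition.

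One sentence in Section 3.0 connects Arm 2 safety to crossover: "The dose of acalabrutinib for these subjects will be determined based on the DLT review of Arm 2".

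**The concern.** Crossover subjects are already enrolled and randomised, so a rule that stops enrolment does not reach them. Followed literally, the protocol can conclude with more than 90% posterior probability that the combination's DLT rate exceeds 30%, close the arm to new subjects, and still start Arm 1 progressors on that combination at their next pembrolizumab visit. That exposes them to the kind of risk the rule was written to limit.

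The point is narrow. A failed or pending DLT review is largely covered, because the crossover dose depends on that review. Whether crossover should stay open after a futility stop is the sponsor's choice and is not questioned. The boundaries, and monitoring Arm 2 only, are not disputed.

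**Working it through.** **Inputs (protocol).** Toxicity prior beta(0.3, 0.7), rule Pr(T > 0.30 | data) > 0.90, looks from n = 10 (Section 5.5). DLT review of 6 subjects per dose level, cleared if the observed rate is below 33% (synopsis; Section 3.7). Maximum 37 subjects per arm (synopsis).

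**1. Reproduce Table 5-1.** With x DLTs in n subjects the posterior is beta(0.3 + x, 0.7 + n − x). The boundary is the smallest x for which the posterior probability that T exceeds 0.30 is above 0.90. At n = 10, x = 5 gives 0.890 (continue) and x = 6 gives 0.969 (stop). At n = 36, x = 14 gives 0.862 (continue) and x = 15 gives 0.924 (stop). Every boundary from n = 10 to 36 matches the table. Observed DLT rates at a boundary include 6/10 = 60%, 8/15 = 53%, 9/20 = 45%, 13/30 = 43% and 15/36 = 42%.

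**2. Does the DLT review reach a Section 5.5 stop?** Section 3.7 places the review after 6 Arm 2 subjects have been treated for at least 4 weeks. Section 5.5 begins at 10. Section 5.1 names clearing the DLT review and not being stopped under Section 5.5 as two separate conditions for adding subjects. A dose can therefore pass the first and fail the second, and Section 3.0 refers only to the first.

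**3. How often would that happen at the starting dose?** Since 2/6 = 33.3%, the review clears with 0 or 1 DLT in 6:

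P(clear) = (1 − p)^6 + 6p(1 − p)^5.

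Given 0–1 DLT in the first 6, an exact binomial recursion is run forward with looks at n = 10 to 36 against Table 5-1. The joint probability is P(clear) × P(stop given clear).

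| True DLT rate p | P(clear) | P(stop given clear) | Joint | Mean n at stop |
|---|---|---|---|---|
| 20% | 0.655 | 0.005 | 0.003 | 20.0 |
| 30% | 0.420 | 0.079 | 0.033 | 23.1 |
| 40% | 0.233 | 0.372 | 0.087 | 23.4 |
| 50% | 0.109 | 0.768 | 0.084 | 21.6 |
| 60% | 0.041 | 0.965 | 0.040 | 18.4 |

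**4. All three dose levels.** A failed review leads to Level −1 and then Level −2. This step assumes that the DLT count restarts at each level and that subjects at failed levels count toward the 37. Each term is the probability of failing the earlier reviews times the joint probability at that level. Totals can differ by 0.001 from the rounded terms.

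- Same DLT rate at every level, 30%: 0.033 + 0.015 + 0.007 = 0.055
- Same rate, 40%: 0.087 + 0.051 + 0.029 = 0.167
- Same rate, 50%: 0.084 + 0.063 + 0.044 = 0.192
- Rates falling by level: about 0.11 for 40/30/20%, 0.11 for 50/30/25%, and 0.035 for 30/20/20%

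The equal-rate totals are best read as the upper end, because they give dose reduction no benefit.

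**5. Number exposed.** This depends on accrual, progression and crossover rates that the protocol does not give, so no count is claimed.

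**The case against.** **No contradiction.** Section 5.5 governs enrolment and Section 3.0 governs treatment after progression, so both can be followed at once and no number is wrong. That is true. The point is a gap in the scope of a safety rule, and is rated accordingly.

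**Other safeguards.** Section 3.11 makes crossover permissive. Under Section 3.12 the investigator, with the medical monitor, "may withdraw any subject from study treatment"; it also says that subjects whose condition changes substantially should be evaluated, and withdrawn if continuing would put them at risk. Section 3.8 provides dose holds and Section 3.14 ongoing AE review. Section 7.0 lists as a ground for termination: "The incidence and/or severity of AEs in this or other studies indicating a potential health hazard caused by the study treatment". These lower the practical risk, and the Section 3.12 evaluation could come before crossover. But they are discretionary, apply subject by subject, or act after dosing starts. None closes crossover when the boundary is met.

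**A deliberate choice.** The current amendment responded to transaminase findings on the combination by adding crossover visits and extending the hepatotoxicity hold to crossover subjects, while keeping crossover open. That shows crossover safety was considered. It equally shows that combination protections were meant to extend to crossover subjects, and no reason is given for leaving Section 5.5 out.

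**The Arm 2 rate may not carry over.** DLTs include events related to either drug, and Section 5.5 counts them in subjects newly starting both. Crossover subjects have already received pembrolizumab. This stands: the 42–60% boundary rates do not estimate crossover risk. They do describe what would have been seen when the protocol still directs new starts.

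**Figure 3-1**, the study schema, is not reproduced in the text reviewed and could not be checked for a crossover condition.

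**Conclusion.** The concern holds as a point to consider. No text that could be read closes or conditions crossover once the Section 5.5 toxicity boundary is met, and the DLT-review link does not reach a later stop at a dose already cleared.

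The triggering sequence is uncommon: at most 8.7% of trials at the starting dose over the true DLT rates examined. It rises to 16.7% at a true rate of 40% and 19.2% at 50% across all levels, but only if the DLT rate does not fall with dose and the count restarts at each level. These are probabilities of a stop, not of harm. Table 5-1 is correct as printed. Confidence is medium, given the discretionary safeguards and the missing schema.

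**What to change.** State in Sections 3.0, 3.11 and 5.5 that no subject newly crosses over to the combination once the Section 5.5 toxicity boundary has been met. To clarify the existing dose link in Section 3.0, add that no crossover begins while no acalabrutinib dose level has cleared the Arm 2 DLT review. Leave the boundaries and Table 5-2 unchanged.

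The cost is one sentence in each of three sections, with no change to sample size, boundaries or data collection. The downside is that, after a toxicity stop, some Arm 1 progressors lose access to crossover and some data for the exploratory crossover objective in Section 2.3 are lost.
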